## **3 STUDY IMPLEMENTATION**

### **3.1 STUDY DESIGN**

This is a randomized, prospective pilot study of TARP peptide vaccination in HLA-A\*201 patients with Stage D0 prostate cancer. HLA-A\*201 positive eligible patients with *no evidence*

of brain, visceral or bony metastatic disease, a non-castrate testosterone level  $\geq 50$  ng/dL (prior ADT allowed; must be  $\geq 6$  months since last dose of ADT), and a PSADT  $> 3$  months and  $\leq 15$  months will be randomized to receive TARP peptides with Montanide® ISA 51 VG adjuvant plus GM-CSF administered by deep subcutaneous (SC) injection or autologous, TARP peptide-pulsed dendritic cells administered intradermally (ID).

TARP peptides or TARP-pulsed dendritic cells will be administered every three weeks at weeks 3, 6, 9, 12, and 15 for a total of five vaccinations with a booster dose of TARP vaccine given at Weeks 48 and 96. PSADT will be calculated in months at the following study time points: Pre-Enrollment/Baseline, weeks 12, 24, 36, 48, 60, 72, 84, 96, 108, 120, 132, and 144. PSADT will be calculated using the Memorial Sloan-Kettering Cancer Center cancer information prostate nomogram for PSA doubling time found at:

<http://www.mskcc.org/mskcc/shared/forms/Nomograms/flash/load.cfm?type=Prostate&width=586&height=505&title=Prostate%20Nomogram> as recommended in the Prostate Specific Antigen Working Group Guidelines. Cumulative PSA values within 12 months inclusive of the study time point will be used for calculation of the baseline/Week 0 PSADT.

Exploratory comparisons of percent change in PSADT will be done among the following time points:

[figure not shown]
- Pre-Enrollment/Baseline PSADT vs. Week 12 PSADT
- Pre-Enrollment/Baseline PSADT vs. Week 24 PSADT
- Pre-Enrollment/Baseline PSADT vs. Week 36 PSADT
- Pre-Enrollment/Baseline PSADT vs. Week 48 PSADT
- Week 24 PSADT vs. Week 36 PSADT
- Week 36 PSADT vs. Week 48 PSADT
- Additional exploratory analyses of PSADT will be performed of Pre-Enrollment/Baseline PSADT vs. Weeks 60, 72 and 96 and Week 48 PSADT vs. Weeks 96, 108 and 144 PSADT.

Week 24 PSADT responders will be allowed to receive an additional dose of TARP peptide vaccine at Week 36. All patients will receive a booster of vaccine at Weeks 48 and 96.

Assessment of humoral and cellular immune responses to TARP peptide vaccination will be performed at weeks 0, 12, 18, 24, 36, 48, 60, 96, 108, 120, 132, and 144. Antigen-specific T-lymphocyte responses will be assessed by tetramer staining, IFN- $\gamma$  ELISPOT and  $^{51}\text{Cr}$  release CTL assays following exposure to native wild type and epitope-enhanced TARP peptides.

The schema for treatment is detailed below.

### 3.1.1 Study Schema

### 3.2 VACCINE ADMINISTRATION

Following apheresis to remove peripheral blood monocytes for dendritic cell preparation as well as peripheral blood mononuclear cells for flow cytometry and immunologic studies at their week 0 visit, all patients will undergo intranasal vaccination with live attenuated influenza vaccine (FluMist™) when seasonally available. Attenuated influenza vaccine is being administered as a control vaccine to characterize the patient's innate ability to generate immune responses to vaccination. Conserved HLA-A\*0201 restricted cellular and humoral responses to flu matrix peptides have been extremely well characterized regarding antibody titers and the range of ELISPOT responses that are typically observed in normal healthy individuals. Following receipt of the intranasal flu vaccine, patients will be immediately discharged to home and precautions will be taken to minimize the risk of potential transmission to other Clinical Center patients as outlined in Section 9.5

Because live attenuated influenza viruses replicate in the nasopharynx of recipients and can be shed in respiratory secretions, the possibility exists that the vaccine viruses can be transmitted to susceptible individuals who have not received the vaccine. Studies in children 8-36 months of age attending daycare who were randomized to receive a single dose of influenza virus vaccine live intranasal or placebo indicated that 80% of vaccine recipients shed at least 1 vaccine strain; the mean duration of shedding was 7.6 days (range: 1-21 days). The frequency and duration of shedding of vaccine virus strains by individuals 5-49 years of age who receive influenza virus

vaccine live intranasal have not been established. Consequently, study patients will return to the CC at study week 3 which should provide an adequate window to ensure that recipients are unlikely to be shedding attenuated viral vaccine strains.

Patients in Arm A will receive an admixture of the wild-type and epitope-enhanced TARP peptides emulsified with Montanide® ISA 51 VG and GM-CSF administered by deep subcutaneous (SC) injection. Patients in Arm B will receive peptide-pulsed dendritic cells administered intradermally in two vaccination sites. Each peptide will be pulsed on dendritic cells separately in order to assure adequate binding of the peptide and cells will not be washed to remove free peptide after pulsing. Following verification of mature dendritic cell validation markers and release standards, the separately peptide-pulsed dendritic cells will be recombined for administration. Refer to [Appendix 2](#) for details concerning the production of peptide –pulsed dendritic cells by the NIH Clinical Center Department of Transfusion Medicine under the supervision of Drs. [name], [name], [name], & [name].

For both groups vaccinations will be administered at weeks 3, 6, 9, 12 and 15 for a total of five vaccinations with a booster dose of vaccine at Weeks 48 and 96. Patients will be monitored for immediate adverse event vaccine reactions (VS, clinical assessment) for 1 hours following their first TARP peptide vaccine dose. If no adverse reactions are observed with the first vaccination, patients will be monitored for 15 minutes for all subsequent vaccinations. If adverse reactions are observed following the first vaccine, the duration of post-vaccination monitoring with subsequent vaccinations will be determined by the Principal Investigator and Lead Associate Investigator as clinically indicated depending on the severity of the initial vaccine reaction. Since this protocol involves TARP vaccination in humans for the first time, enrollment will be staggered to allow for safety monitoring. For the first 3 patients on each study arm, enrollment of the next patient can only proceed until the preceding study subject is 2 weeks status-post their first vaccination. If no adverse events are observed in the two week window following the first vaccination in these 6 patients, enrollment of additional patients may proceed as quickly as is logistically feasible. Cells used for subsequent dendritic cell maturation will be derived from monocytes frozen during the initial apheresis.

### **3.3 TREATMENT MODIFICATIONS AND IMMUNIZATION STOPPING RULES**

No dose modifications will be made in patients receiving vaccination. Subjects will cease to receive immunization if they experience dose-limiting toxicity (DLT). Toxicity will be graded according to NCI Common Terminology Criteria for Adverse Events (CTCAE) v3.0 ([http://ctep.info.nih.gov/reporting/ctc\\_v30.html](http://ctep.info.nih.gov/reporting/ctc_v30.html))

#### **3.3.1 Immunization-Related Dose Limiting Toxicity (DLT)**

Immunization-related DLT is defined by the parameters outlined below attributed by the Principal Investigator or Protocol Chairperson as possibly, probably or definitely related to vaccine administration:

- 3.3.1.1 Any Grade 2 or Grade 3 or greater allergic/hypersensitivity reaction
- 3.3.1.2 Any Grade 2 or greater rash consistent with erythema multiforme.
- 3.3.1.3 Grade 3 or greater hematologic or non-hematologic toxicity, excluding lymphopenia. Abnormal laboratory studies will be repeated to verify toxicity
- 3.3.1.4 Grade 3 or greater acute vascular leak syndrome: respiratory compromise or fluids indicated.

3.3.1.5 The following Grade 3 reactions commonly associated with immunization **will** be dose-limiting:

- Injection site reactions: ulceration or necrosis that is severe; operative intervention indicated.
- Skin rash/desquamation: severe, generalized erythroderma or macular, papular or vesicular eruption; desquamation covering  $\geq 50\%$  BSA.
- Urticaria: intervention indicated for  $\geq 24$  hrs.

3.3.1.6 The following Grade 3 reactions commonly associated with immunization **will not** be dose-limiting:

- Pruritis/itching: intense or widespread and interfering with ADL lasting  $\leq 72$  hrs
- Fatigue: severe fatigue interfering with ADL lasting  $\leq 72$  hrs
- Fever:  $> 40.0^{\circ}$  C for  $\leq 24$ hrs
- Local lymphadenopathy lasting  $\leq 1$  week

### 3.3.2 Stopping for Excessive toxicity

If more than one of the first nine subjects in either arm of the trial experiences dose limiting toxicity, enrollment to that arm will cease pending discussion and review with the FDA and the IRB.

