For each arm, using an acceptable immunologic response rate of 40% ( $p_1=0.40$ ) and an unacceptable rate of 10% ( $P_0=0.10$ ) and using a two-stage optimal design (Simon R, *Controlled Clinical Trials* 10:1-10, 1989) with  $\alpha = 0.05$  and  $\beta = 0.10$ , we will initially accrue 9 patients in each arm. An unacceptable response rate of 10% (or less) and an acceptable response rate of 40% were determined based on historical clinical trial response rates to vaccines and immune-based therapies for cancer. If 0-1 patients develop an immunologic response as defined in Section 5.2.1, then no further patients will be enrolled. If 2 or more of these 9 patients develop an immunologic response, we will accrue 11 additional patients for a maximum total of 20 patients per arm. If 2-4 of 20 has an immunologic response, then the results from this arm will be considered inadequate for further investigation. If 5 or more of these 20 has an immune response, we will be able to conclude that the vaccine on the given arm is worthy of further development in this population on the basis of immune response. Under the null hypothesis ( $p_0=0.20$ ), the probability of early termination is 77%.

There is no requirement that only one arm be selected for further development; should both arms demonstrate adequate immunologic responses, then future studies will consider either or both arms depending on immune responses, feasibility, toxicity and other outcomes such as PSADT.

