As stated in Section 3.3.2, an early stopping rule will be used to ensure that the study subjects do not have exposure to excessive toxicity: If more than one of the first nine subjects on a given arm experiences dose limiting toxicity (defined in Section 3.3.1), enrollment will cease for that arm and revisions to the treatment will be discussed with the IRB and FDA. This is because 1/9 has an upper one-sided 90% confidence interval limit of 37%, while 2/9 has an upper one-sided 90% confidence interval limit of 49%; the former would be marginally acceptable as a rate of toxicity while the latter is not. In addition, any unusually severe toxicity noted may result in temporary suspension of accrual pending re-evaluation of the agent. All toxicities noted will be tabulated by type and grade, for each arm. Any such toxicities that appear in at least 5 patients on either arm will also have the distribution of grades of that toxicity compared between the arms using an exact Cochran-Armitage test.

The percent of patients who meet PSADT response criteria as outlined in section 5.2.2 will also be evaluated as a secondary endpoint. In addition, exploratory comparisons of PSADT among study time points will be performed as outlined in Sections 3.1 and 5.2.2. Given that there will be 6 separate comparisons of PSADT, we will only report differences with  $p < 0.01$  as being statistically significant while other differences with  $0.01 < p < 0.05$  will be considered to be trends. Appropriate 95% confidence intervals will be constructed and reported which takes into consideration the two-arm nature of the design. No formal comparison will be undertaken since the study does not have adequate power to address this comparison properly.

It is expected that 1-2 patients per month may be enrolled onto this study. Based on accrual of 18-20 patients per year, accrual should be completed in approximately 2 to 2.5 years if all 40 patients were to be required. To allow for the possibility of inevaluable patients, an accrual ceiling of 43 will be used.

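### The only numeric toxicity rule counts dose-limiting toxicities in the first nine subjects of each arm, so those in patients 10 to 20 never count toward a required halt

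*Combined protocol and SAP*

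**What the plan says.** Section 3.3.2 stops enrollment to an arm, pending FDA and IRB review, on this condition: "If more than one of the first nine subjects in either arm of the trial experiences dose limiting toxicity". Section 6.2 gives the same trigger ("If more than one of the first nine subjects on a given arm experiences dose limiting toxicity") and bases it on confidence limits: "1/9 has an upper one-sided 90% confidence interval limit of 37" percent, and "2/9 has an upper one-sided 90% confidence interval limit of 49" percent. Of these two results it says that "the former would be marginally acceptable as a rate of toxicity while the latter is not".

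Accrual per arm is set in section 6.2. First, "we will initially accrue 9 patients in each arm". If at least two of the nine respond immunologically, "we will accrue 11 additional patients for a maximum total of 20 patients per arm". No DLT count or rate is given for those 11.

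One arm-level safeguard in section 6.2 has no patient limit: "any unusually severe toxicity noted may result in temporary suspension of accrual pending re-evaluation of the agent". Elsewhere:

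- Section 3.3 stops vaccination in a subject who has a DLT.
- Section 3.2 staggers enrollment for the first three patients per arm, because this is the first use of TARP vaccination in humans.
- Section 7.4.1 provides continuous review by the investigators, with no DSMB.
- Sections 7.2 and 7.3 set reporting to the IRB, the Clinical Director and the sponsor.

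**The concern.** Safety is a primary objective (sections 1.1.1 and 6.2). The reasoning behind the rule concerns an arm's DLT rate, and nothing in it ceases to apply once nine patients are enrolled. Yet more than half of a full arm falls outside the count. An arm with 0 or 1 DLT in its first nine subjects can then accumulate any number of DLTs in the next 11 without a required pause. The discretionary clause responds to severity, so an excess of ordinary Grade 3 events need not trigger it. At stake is whether a first-in-human arm could complete accrual with an observed DLT proportion that the plan refused at nine patients, with the decision to continue left to investigators who have no stated threshold.

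**Working it through.** **Inputs.** From sections 3.3.2 and 6.2: the rule (2 or more DLTs in subjects 1 to 9), limits of 37% and 49%, 9 patients then 11, 20 in total. The documents give no true DLT rate p, so p is assumed over a range.

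**1. The plan's own figures.** The exact (Clopper-Pearson) one-sided 90% upper limit for x of n is the 0.90 quantile of Beta(x+1, n−x). It gives 36.8% for 1/9 and 49.0% for 2/9, so the stated 37% and 49% reproduce.

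**2. Share outside the rule.** 20 − 9 = 11 patients, and 11/20 = 55%.

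**3. Passing the first-nine rule.** P(pass) = (1−p)^9 + 9p(1−p)^8.

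- p = 0.20: 0.1342 + 0.3020 = 0.436
- p = 0.25: 0.0751 + 0.2253 = 0.300
- p = 0.30: 0.0404 + 0.1556 = 0.196

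Expected DLTs in the next 11 are 11p = 2.2, 2.75 and 3.3.

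**4. Passing and finishing above 2/9.** 4/20 = 20% lies below 22.2% and 5/20 = 25% lies above it, so the event is 5 or more of 20. With Y ~ Bin(11, p), the joint probability is P(0 in 9)·P(Y≥5) + P(1 in 9)·P(Y≥4).

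- p = 0.20: 0.1342×0.0504 + 0.3020×0.1611 = 0.055; divided by 0.436, 12.7% given a pass
- p = 0.25: 0.0751×0.1146 + 0.2253×0.2867 = 0.073; divided by 0.300, 24.4%
- p = 0.30: 0.0404×0.2103 + 0.1556×0.4304 = 0.0755; divided by 0.196, 38.5%

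At lower true rates the joint probability is small: 0.8% at p = 0.10 and 0.05% at p = 0.05.

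**5. The same question by upper limit.** The limits are 36.1% for 4/20, 41.5% for 5/20, 46.7% for 6/20 and 51.8% for 7/20. Only 7/20 exceeds the 49% attached to 2/9. The joint probability of passing and reaching 7/20 or more is 0.4/0.8/1.3% at p = 0.20/0.25/0.30 (0.9/2.8/6.7% given a pass).

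**6. Carrying 2/9 forward from patient 10.** The smallest whole number at or above 2n/9 is 3 for n = 10 to 13 (2.22 to 2.89), 4 for n = 14 to 18 (3.11 to 4.00) and 5 for n = 19 to 20 (4.22 to 4.44). Exact sequential calculation over 20 patients gives the chance of ever meeting the criterion in one arm:

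| True DLT rate | Rule as written | First-nine rule plus 2/9 from patient 10 |
|---|---|---|
| 5% | 0.0712 | 0.0775 |
| 10% | 0.2252 | 0.2616 |
| 20% | 0.5638 | 0.6746 |
| 30% | 0.8040 | 0.9100 |

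The increase at 20% (11.1 points) exceeds the 5.5% in step 4 because an arm can cross the line during accrual and finish below it.

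Steps 3 to 6 treat patients as independent, assume that each DLT is known before the next patient enters, and assume that the arm also passes the stage 1 immunologic test.

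**The case against.** The strongest reply is that patients 10 to 20 are not unprotected. Each subject with a DLT stops vaccination. The discretionary clause applies throughout. The investigators review toxicity reports weekly or every two weeks, and the FDA receives six-monthly summaries (section 7.4.1). An Unanticipated Problem includes events unexpected in frequency (section 7.1.10) and must reach the IRB and Clinical Director within 7 days (section 7.2.1). This stands, so a reader who infers that oversight ends at patient 9 goes too far. None of these provisions, however, contains a count or rate that obliges a halt.

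Nor does the rule lapse in time at the ninth enrollment. It names subjects, so a late DLT in one of the first nine, including after a booster at week 48 or 96, can still halt enrollment during stage 2.

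A reader might also infer that arms can readily run past the 49% upper limit, or that 37% is the plan's ceiling. The documents support neither. On the upper-limit reading, 7/20 is needed, and that is rare (step 5). Section 6.2 calls 37% marginally acceptable and 49% not, and does not place a ceiling between them. A 37% ceiling applied throughout accrual would also be unworkable: 0/4 already has an upper limit of 43.8%, and one DLT among eight has 40.6%.

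Finally, the existing rule does much of the work. It halts 56/70/80% of arms at true rates of 20/25/30%, and 97.8% at 49%. Extending it is a design choice and does not correct a breach of the plan's own rules. That is fair, and it limits the weight of the point.

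**Conclusion.** The point holds as a gap in the numeric rule and should be addressed. DLTs in 11 of 20 patients per arm never count toward a required halt, so an arm can finish at 25% or more, above the 22% observed rate that the plan rejects at nine patients. The exposure is moderate: a joint probability of 5.5/7.3/7.5% per arm at assumed true rates of 20/25/30%, and under 1% at 10% or lower. The conditional 13/24/38% describes only arms that have already passed the first-nine rule and should be read beside the joint figures.

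The conclusion rests on reading the rejected rate as the observed 2/9. It also rests on assumed DLT rates and on the arm continuing to 20 patients. Requiring the stage 1 immunologic response as well could only lower the joint figures if response and toxicity are independent.

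**What to change.** Keep the first-nine rule unchanged. Add to sections 3.3.2 and 6.2 that, from patient 10 on, enrollment to an arm pauses for the same FDA and IRB review if its cumulative DLT proportion reaches 2/9. Arithmetically, that is 3 DLTs at 10 to 13 patients, 4 at 14 to 18 and 5 at 19 to 20. This carries forward the rate that the plan already rejects. Whether it is the right threshold is for the sponsor to confirm, with the operating characteristics stated in section 6.2. The text should also define the denominator (for example, patients vaccinated) and say how DLTs still pending in recent patients are handled. At patient 20 the criterion can prompt review but has no further planned enrollment to pause.

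The change is a sentence or two in each section. The cost is more review pauses per arm: from 7% to 8% at a true DLT rate of 5%, and from 22.5% to 26.2% at 10%. Where toxicity is high, the chance of a pause rises from 56% to 67% at 20% and from 80% to 91% at 30%. Each is a pause for review and need not end the arm.

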### 3.3.3 Delay in Vaccination

Patients who are unable to receive their vaccine injection as scheduled due to adverse events, toxicity or unforeseen personal or medical circumstances and who are otherwise eligible to continue on protocol, may be continued on vaccine therapy provided that their next vaccine is within three weeks of the previous vaccine. Patients will be advised of their options concerning alternative treatments before proceeding with the completion of their study vaccinations. The reason for the change in vaccination schedule will be documented in the patient's chart.

## 3.4 ON STUDY EVALUATION

Refer to [Appendix 1](#) for the Schedule of Clinical, Laboratory and Radiographic Evaluations.

### 3.4.1 Clinical Evaluation

(weeks 0, 3, 6, 9, 12, 15, 18, 24, 36, 48, 60, 72, 84, 96, 108, 120, 132 and 144.)

3.4.1.1 Review of systems and documentation of symptoms

3.4.1.2 Assessment of ECOG Performance Status

3.4.1.3 Vital signs and physical examination

3.4.1.4 Assessment of injection site reactions

3.4.1.5 Provision of Vaccination Report Card to study subject (when TARP vaccine administered)

### 3.4.2 Laboratory Evaluation

(weeks 0, 3, 6, 9, 12, 15, 18, 24, 36, 48, 60, 72, 84, 96, 108, 120, 132, and 144.)

3.4.2.1 CBC with differential and platelets

3.4.2.2 Chemistries (Acute Care Panel, Mineral Panel, Hepatic Panel, total protein, CK, Uric acid, LDH),

3.4.2.3 PSA, testosterone

3.4.3 Radiographic Evaluation

(Weeks 0, 48, 96 and 144. No further restaging unless clinically indicated. )

3.4.3.1 CT Scan of the chest/abdomen/pelvis

3.4.3.2 Bone Scan

3.4.4 Immunologic Responses

(Weeks 0, 12, 18, 24, 36, 48, 60, 96, 108, 120, 132, and 144.)

3.4.4.1 Lymphocyte Subsets: CD4 and CD8 percent and absolute counts (done at Clinical Center)

3.4.4.2 Anti-TARP antibody responses

3.4.4.3 NKT Cell analysis (weeks 0, 12, 18 and 24 only)

3.4.4.4 IFN- $\gamma$  ELISPOT of PBMCs

3.4.4.5 Tetramer staining and  $^{51}\text{Cr}$  release CTL assay of PBMCs

3.4.5 Apheresis

Weeks 0, 24, 48.

3.4.6 Research Specimens for Assessment of Immunologic Responses

3.4.6.1 Cryopreserved PBMCs (6 tubes sodium heparin 10ml GTT) for tetramer, IFN-g ELISPOT and CTL assays. Weeks 0, 3 (FluMist responses), 12, 18, 24, 36, 48, 60, 72, 84, 96, 108, 120, 132 and 144. Note: PBMCs are for storage only at Weeks 72 and 84.

3.4.6.2 Serum Storage (10ml RTT) for anti-TARP antibody responses. Weeks 0, 12, 18, 24, 36, 48, 60, 72, 84, 96, 108, 120, 132 and 144.

3.4.6.3 NKT Cell Analysis (2 tubes 8ml blue tiger top sodium citrate tubes). Weeks 0, 12, 18, 24,

**3.5 CONCURRENT THERAPIES**

3.5.1 Contraindicated Therapies

3.5.1.1 Patients may not receive chemotherapy, hormonal therapy or radiation therapy while on study.

3.5.1.2 Systemic administration of steroids is not allowed with the exception of oral corticosteroids for management of acute allergic reactions or contact hypersensitivity of  $\leq 14$  days duration in patients who require them. Topical steroids as well as intranasal steroids are permitted. Patients must not have received systemic steroids within 14 days to TARP peptide vaccination.

3.5.1.3 Pharmacologic doses of immune modulating agents including IVIG, recombinant cytokines or growth factors.

3.5.1.4 Immunosuppressive agents such as cytotoxic chemotherapy.

3.5.1.5 Other investigational agents.

